- 10 All patients will have a CT-scan with contrast or MRI of thorax, abdomen, and pelvis during screening. Head and neck imaging is also required for patients with squamous cell carcinoma of the head and neck (SCCHN). Imaging of the pelvis is not required for patients with SCCHN but is strongly recommended. If a CT scan or MRI has been performed within 21 days prior to visit Cycle 1 Day 1 as part of standard procedure, it is acceptable as a screening scan for the trial. If there is suggestion of brain metastases/tumors, a CT-scan or MRI of the head and neck will be performed within 21 days prior to the Cycle 1 Day 1 visit. Scans that exceed the 21-day window may be used for trial enrollment with sponsor approval.
- 11 On-treatment imaging will be performed at Week 6 (+7 days), every 6 weeks (±7 days) for 48 weeks, and every 12 weeks (±7 days) thereafter until disease progression is assessed by the investigator (unless the investigator elects to continue treatment [see Section 8.5.1 for conditions of continued treatment]), withdrawal of consent, trial termination by the sponsor, or death, whichever occurs first, regardless of whether patients start a new anti-cancer therapy. Refer to Sections 10.5 and 10.6 of the protocol for RECIST 1.1. and iRECIST imaging and treatment guidelines.
- 12 ECOG status should be assessed before drug administration.
- 13 Adverse events (AEs) and serious adverse events (SAEs) should be reported from the time of signing the informed consent to 60 days (±7 days) after the patient receives the last dose of BNT411, or atezolizumab, or carboplatin, or etoposide, whichever occurs later.

14 Suspected BNT411 related AEs only. Except for Germany and Spain, where AEs related to atezolizumab, carboplatin, and etoposide should also be reported. Furthermore, in Germany only, all SAEs that occur in the patient throughout his or her lifetime should be reported – refer to Table 1-5 and Section 10.3.4 for further details.

- 15 Patients who experience a delay in the administration of BNT411 should return to the clinic at least every 2 weeks (±3 days) and an unscheduled visit should be performed and reported in the eCRF. Unscheduled visit assessments should be performed at the investigator's discretion. For information on COVID-19 vaccination during the trial, see Section 10.9.
- 16 After discontinuation of chemotherapy, atezolizumab will be administered in combination with BNT411.

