# 2.3.2 Potential Risks Associated with BNT411 in Combination with Atezolizumab, Carboplatin, and Etoposide

As this is the first trial in humans, the risk of synergistic and/or potentiating toxicities when BNT411 is combined with atezolizumab, carboplatin and etoposide cannot be completely ruled

out. Therefore, the trial seeks to mitigate this risk by implementing a bifurcated trial design to start combination dose escalation. The combination dose escalation will only occur after reasonable data for BNT411 are generated in monotherapy dose escalation. Additionally, the dose level to start the combination dose level and at any given time thereafter will always be one dose level lower than in monotherapy dose escalation. This should mitigate such a potential risk for unknown synergistic and/or potentiating toxicities. Supporting data from preclinical studies of BNT411 in combination with cytotoxic agents also do not suggest any other risks seen in BNT411 monotherapy. The sponsor is also currently performing further preclinical experiments of BNT411 in combination with more chemotherapy agents and anti-PD-L1 antibody.

No indications of organ-specific autoimmunity have been identified for BNT411, or for any other imidazoquinoline compounds. In this trial (Part 1B, Part 2) BNT411 is combined with atezolizumab, which is known in line with its mode of action to be associated with organ-specific autoimmunity and consequently with immune-related adverse events (irAEs). Therefore, irAEs and their management are specifically addressed by this trial protocol, even though the risk of them induced by single agent BNT411 is considered as very low.

In conclusion, the non-clinical and literature data collected so far do not show any potential unacceptable toxicities that cannot be mitigated or managed in the clinical setting. The anticipated benefits of BNT411 in patient populations with high unmet medical needs outweigh the potential risks with the compound.

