# 6 Trial Treatment

# 6.1 Trial Treatment(s) Administered

Trial treatment may refer to the following compounds, either:

- 1. BNT411, and/or
- 2. Atezolizumab, and/or
- 3. Carboplatin, and/or
- 4. Etoposide.

BNT411 is a highly potent and selective small molecule TLR7 agonist of the imidazoquinoline family being developed by BioNTech and is a new investigational agent to be tested clinically in this trial. In all countries participating in the trial, BNT411 is considered as investigational medicinal product (IMP).

Atezolizumab is a PD-L1 blocking antibody indicated for the treatment of patients with various cancer diagnoses at different stages. Atezolizumab was first approved by FDA on May 18, 2016 to treat urothelial carcinoma, and similar positive opinion by European Medicines Agency (EMA) followed in July 2017. Carboplatin is a platinum coordination compound and etoposide is a topoisomerase inhibitor. They are both cytotoxic agents used in various chemotherapy regimens to treat many cancer indications. On March 18, 2019, the FDA approved atezolizumab in combination with carboplatin and etoposide, for the first-line treatment of adult patients with ES-SCLC. Since then, it has become a standard-of-care treatment in the US. In October 2019, EMA issued similar positive opinion for the combination. For the purpose of this trial, in the USA and UK, atezolizumab, carboplatin and etoposide are considered as non-investigational medicinal products (NIMPs). However, the individual drugs are considered as IMPs in Spain and Germany at the request of the competent authorities due to their use in combination with BNT411.

Information relating to COVID-19 vaccinations including a risk-benefit assessment and guidance for vaccination during this clinical trial is provided in Sections 10.8 and 10.9.

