#### **Period of observation:**

- The period of observation starts after informed consent has been obtained. After informed consent, all AEs and SAEs should be reported until 60 days after the last dose of trial treatment.
- AEs occurring later than 60 days after the last trial treatment must only be documented if a relationship to trial treatment or trial procedure is suspected.

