#### **AE and SAE Recording**

- SAEs will continue to be reported until 60 days after the last dose of IMP. All SAEs for which the investigator suspects a relationship to IMP or trial procedure have to be reported to the safety contact (given in Section 10.3.4), even if they occur after the end of the period of observation. In Germany, all SAEs, regardless of relatedness, that occur in a patient throughout his or her lifetime should be reported (Section 12.2.1).
- Investigators will seek information on AEs at each subject contact. All AEs, whether reported by the subject or noted by trial personnel, will be recorded in the subject's medical record and on the AE eCRF.
- The investigator should follow each AE until the event has resolved to baseline grade
  or better, the event is assessed as stable by the investigator, the subject is lost to followup, or the subject withdraws consent. Every effort should be made to follow all SAEs
  considered to be related to trial treatment or trial-related procedures until a final
  outcome can be reported.

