8.5.2 Adverse events

This section includes the description of the analysis planned for the primary endpoints on this trial.

AEs will be coded using the most recent version of Medical Dictionary for Regulatory Activities (MedDRA®) coding system version 26.0 or higher to get a SOC and PT for each AE and graded for severity using NCI CTCAE v5.0. In case a patient has an AE with missing relationship status, the event will be assumed to be related and associated with the treatment received in the summaries (will be listed as collected in the listings). No imputation for missing NCI-CTC grades will be performed.

A treatment-emergent AE (TEAE) is defined as any AE with an onset date on or after the first administration of trial treatment (BNT411 in part1A and BNT411, atezolizumab, carboplatin, and etoposide in Part 1B) (if the AE was absent before the first administration of trial treatment) or worsened after the first administration of trial treatment (if the AE was present before the first administration of trial treatment). AEs with an onset date more than 60 days after the last administration of trial treatment will be considered as treatment-emergent only if assessed as related to trial treatment (BNT411 for Part 1A and BNT411, atezolizumab, carboplatin, and etoposide for Part 1B) by the investigator.

Treatment-emergent AEs will be summarized by cohort and trial part and total within trial part. In addition, treatment-related TEAEs will be summarized by cohort and trial treatment (BNT411, atezolizumab, carboplatin, and etoposide) within trial part.

Only TEAE data will be summarized for the Safety set for each trial part (Part 1A and Part 1B). Non-TEAEs will be listed only.

Dose-limiting toxicities

In general, a DLT for a drug or other treatment is defined as one or more AEs that prevents an increase of the dose level of that treatment (for details on dose escalation decision rules see Appendix 5).

Serious AEs (SAEs), non-serious grade ≥ 3 AEs and clinically significant abnormal laboratory values grade ≥ 3 will be collected and assessed for DLTs (for each dose level during the first cycle). Common Terminology Criteria for Adverse Events (NCI CTCAE) v.5.0 will be used to grade the intensity of AEs.

More details regarding DLTs can be found in the Section 6.6 of the CTP.

For the additional rules and considerations of MTD and RP2D other than what was already defined in Section 1.1, see Section 4.1.1.2 of the CTP.

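### Part 1B safety collection is worded inconsistently: the 60-day SAE window runs from either IMP or any trial treatment, and late AEs related only to a backbone drug are required by the Schedule of Activities in Germany and Spain but not in the USA and UK

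*Protocol*

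**What the plan says.** Atezolizumab, carboplatin and etoposide are called the backbone drugs here.

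- **Drug status.** Protocol 6.1 lists all four drugs as trial treatment. It adds that "in the USA and UK, atezolizumab, carboplatin and etoposide are considered as non-investigational medicinal products (NIMPs"), whereas Spain and Germany treat them as IMPs.
- **60-day window.** For Part 1B, Table 1-2 footnote 13 collects AEs and SAEs until 60 days "after the patient receives the last dose of BNT411, or atezolizumab, or carboplatin, or etoposide, whichever occurs later". Protocol 10.3.3, under Period of observation, likewise counts 60 days from the last trial treatment for AEs and SAEs. Under AE and SAE Recording, the same section says "SAEs will continue to be reported until 60 days after the last dose of IMP".
- **After the window.** Under Period of observation, AEs later than 60 days "must only be documented if a relationship to trial treatment or trial procedure is suspected". The sentence on late SAEs, under AE and SAE Recording, refers to IMP or trial procedure instead.
- **Survival follow-up by country.** Footnote 14 reads: "Suspected BNT411 related AEs only. Except for Germany and Spain, where AEs related to atezolizumab, carboplatin, and etoposide should also be reported". Table 1-5 gives the USA and UK BNT411-related and procedure-related events. Spain adds events related to each backbone drug. Germany adds those and all SAEs. The column for the time beyond trial closure follows the same pattern for SAEs.
- **Analysis.** SAP 8.5.2 states that an AE starting more than 60 days after the last administration is "considered as treatment-emergent only if assessed as related to trial treatment (BNT411 for Part 1A and BNT411, atezolizumab, carboplatin, and etoposide for Part 1B"), relatedness being the investigator's judgement. Protocol 9.4.2 has the same rule and also defines trial treatment as all four drugs.

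**The concern.** A US or UK site cannot follow both 10.3.3 and footnote 14 for a late event that it attributes to a backbone drug alone. One rule asks for the event; the other leaves it out. The TEAE definition then counts whatever was collected, so the same definition is applied to two collection regimes.

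The endpoint affected is primary: TEAEs by relationship. Protocol 2.3.2 does not exclude "the risk of synergistic and/or potentiating toxicities when BNT411 is combined with atezolizumab" and chemotherapy. It also ties immune-related events chiefly to atezolizumab, so attribution to a backbone drug alone is a foreseeable category. SAP 8.5.2 tabulates related TEAEs separately for each of the four drugs, by cohort and in total within Part 1B. No safety table is split by country, and SAP Appendix 1 does not mention the difference.

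The IMP wording raises a second problem. Read literally, it gives US and UK sites an SAE cut-off that can fall while a backbone drug is still being given.

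**Working it through.** The plan gives no figure to reproduce. The check sets the rules side by side, with one day count.

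**1. The 60-day SAE window in Part 1B**

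| Place | Clock runs from last dose of | Meaning in USA/UK | Meaning in Spain |
|---|---|---|---|
| 10.3.3, AE and SAE Recording | IMP | BNT411 | any of four drugs |
| 10.3.3, Period of observation | trial treatment | any of four drugs | any of four drugs |
| Table 1-2 footnote 13 | latest of four drugs | any of four drugs | any of four drugs |

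In Germany the window does not matter for SAEs, because all SAEs are reportable for life.

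Let B be the day of the last BNT411 dose and C the day of the last backbone dose. For a US or UK patient:

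- IMP rule ends on day B + 60.
- Trial-treatment rule ends on day max(B, C) + 60.
- Difference = max(0, C − B), which is zero if all drugs stop together.

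Illustration with an assumed patient: BNT411 is stopped after Cycle 1 Day 2, and the backbone is completed to etoposide on Cycle 4 Day 3, with nothing later. B = 2 and C = 3 × 21 + 3 = 66.

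- IMP rule: 2 + 60 = day 62, before the last etoposide dose on day 66.
- Trial-treatment rule: 66 + 60 = day 126.
- Difference: 126 − 62 = 64 days = 66 − 2.

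The protocol provides for this situation. Table 1-2 footnotes 1 and 27 and section 7.2.2 schedule separate visits when the backbone drugs stop 21 days or more after BNT411. Section 6.6.3.2 has a case in which BNT411 is discontinued and the other drugs are dose-modified.

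**2. An event more than 60 days after the last trial treatment, attributed only to a backbone drug**

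| Rule | USA/UK | Spain | Germany |
|---|---|---|---|
| 10.3.3, Period of observation | document | document | document |
| Footnote 14 and Table 1-5, survival follow-up | not required | report | report |
| 10.3.3, late SAEs (IMP wording) | not required | report | all SAEs |
| Table 1-5, beyond trial closure (SAEs) | not required | report | all SAEs |
| 8.7.1, SAE learned of after discharge | notify | notify | notify |
| 9.4.2 and SAP 8.5.2 | counts as TEAE | counts as TEAE | counts as TEAE |

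The conflict lies in the first column. For late SAEs in the USA and UK, the IMP sentence agrees with Table 1-5; it is the Period of observation rule and the TEAE definition that differ from both. The SAP holds both sides itself, because its Appendix 4 (Table 6, footnote 14) repeats the country rule.

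The country rule may also come into play before day 60. Section 7.2.2 moves a patient to survival follow-up once new anti-cancer treatment starts, although footnote 13 makes no exception for this.

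**3. What is not affected**

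Table 1-5 requires all AEs, SAEs included, in every country during screening, treatment and safety follow-up. BNT411-related events are collected everywhere afterwards. DLTs come from Cycle 1, so the DLT evaluation set and the MTD do not depend on any of these rules.

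**The case against.** The strongest reply is that the split is deliberate. It follows IMP status, which the competent authorities in Spain and Germany requested. The version 3.0 change history records that 10.3 moved from IMP to trial treatment except in the section on SAE reporting after the last IMP dose. This explains where the wording came from. It does not reconcile it with footnote 13, with the Period of observation rule that now covers SAEs, or with a TEAE definition that has no country limit.

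A reader might infer that combination toxicity is followed in Germany and Spain but not in the USA and UK. The documents do not support that: all AEs and SAEs are collected everywhere through safety follow-up, whatever the drug.

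A reader might also infer that US and UK SAE reporting stops during atezolizumab treatment. Only one sentence says so. Footnote 13, Table 1-5 and the Period of observation rule say otherwise, and 8.7.1 sends sites to the Schedule of Activities.

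Nor can one say that late backbone-related events are never recorded in the USA and UK. Section 10.3.3 still asks for them, and 8.7.1 requires notification of SAEs learned of after discharge and judged related to trial treatment, though without active search and not for non-serious AEs. The causality guidance also classes an event as related when other drugs could explain it too, so an event with plausible BNT411 involvement is collected everywhere.

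On impact, the analyses are descriptive, relatedness is shown by drug, and such events may be few. All of this stands. It narrows the point but does not remove the contradiction.

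**Conclusion.** The contradiction is in current text and should be corrected; its scope is narrow.

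- **SAE window.** The IMP sentence conflicts with the other sentence in 10.3.3 and with footnote 13. If followed literally in the USA or UK, it shortens the window by the number of days the backbone drugs outlast BNT411.
- **Late AEs.** Part 1B TEAEs that start more than 60 days after the last trial treatment and are attributed solely to a backbone drug are collected in Germany and Spain. The Schedule of Activities does not require them in the USA and UK. A cohort's count of these events, and any total that includes them, therefore depends on its country mix.

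No percentage of lost events can be given: the documents state neither the country mix, nor the rate of such events, nor which of the conflicting rules sites followed. The 64-day figure rests on one assumed patient and is not an estimate for the trial.

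**What to change.** 1. In Protocol 10.3.3, under AE and SAE Recording, replace IMP with any trial treatment in both places: the 60-day window and the sentence on late related SAEs. Changing only the first would leave late SAEs dependent on country.
2. For Part 1B, align footnote 14 and the USA and UK entries of Table 1-5, for survival follow-up and beyond trial closure, with the late-AE rule in 10.3.3. Update the copy in SAP Appendix 4.
3. For data already collected, keep the TEAE definition in SAP 8.5.2. Show Part 1B TEAEs with onset more than 60 days after the last trial treatment and related only to a backbone drug separately by country. Add a note that the Schedule of Activities did not require them in the USA and UK, and record this in SAP Appendix 1. Removing such events from the counts is not advisable: they were validly collected and both documents define them as TEAEs.

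The cost is a few sentences in each document and a few more related-event reports at 12-weekly contacts that already take place. Step 3 may matter most in practice, since Protocol 4.5 lets the medical monitor release patients from the schedule once data collection is considered complete.

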## Table 1-6: Vital Signs during Parts 1A and 1B

Patients should be monitored for a minimum of 6 hours in the clinic after each administration of BNT411.

Vital signs are measured after BNT411 infusion at the following time points (further assessments can be done at the discretion of the investigator):

BNT411 pre-infusion (up to 30 min before infusion)
15 min after start of infusion (±5 min)*
30 min after end of infusion (±5 min)
60 min after end of infusion (±10 min)
120 min after end of infusion (±15 min)

\*If infusion lasts for more than 60 minutes, vital signs should be assessed every 15 minutes (± 5 minutes) for the remaining duration of the infusion.

Table 1-7:	Riomarker tal	ble – in Part 1A	
rabie i-/:	Diomarker ta	Die – in Part IA	

Treatment Cycle	Screening		Cycle 1-2				Cycle 3-N	Treatment discontinuation	Unscheduled
Day/Week	≤21 days prior to Visit C1 (D1)	D1	D2	D 3	D8	D15	D16	-	-
Visit window		-	1h	2h	±D1	±D1	±D3	-	-
Tissue compartment									
Tumor FFPE sample	$X^1$								
Tumor biopsy	$X^2$						X 	$X^2$	$X^2$
Blood compartment									
Cytokines					$X^3$			X 	$X^3$
Immune Phenotyping		X 	X 	X 	$X^4$	X 	X 	X 	X 
TCR profiling		X5					X 	X 	X 

- 1 A formalin-fixed paraffin-embedded (FFPE) tumor tissue sample (for e.g., immunohistochemistry, tumor mutational burden) must be obtained from each patient from the latest available archival tumor tissue. If such tissue cannot be provided, the sponsor approval of enrollment is needed. Details regarding the preparation of slides and number of slides to be prepared will be described in the lab manual.
- 2 An optional fresh tumor biopsy (aspirates are not acceptable) which is collected before Cycle 1, Day 1, preferably derived from advanced stage disease. This biopsy needs to contain tumor tissue and is taken after failure/stop of last prior treatment at screening or before first administration of BNT411. Additionally, biopsies should be collected at Week 6 ([+7 days], i.e., after 2 cycles of BNT411) and at disease progression or treatment discontinuation if it is considered feasible without a risk of complications for the patient. If deemed necessary by the investigator, the patient may be called in for an unscheduled visit, optional additional tumor biopsies may be collected if patients have unscheduled biopsies or tumor tissue resection during the course of the trial. Details to the preparation of fresh tumor biopsies will be described in the lab manual.
- 3 Cytokine samples will be taken at the same time points given for PK sampling with the exception of "end of infusion"—please refer to Table 1-3. Furthermore, cytokine samples will be taken at disease progression or treatment discontinuation. If an adverse event (AE) of cytokine release syndrome (CRS) is suspected, cytokines should be obtained at an unscheduled visit to confirm diagnosis.
- 4 Immune phenotyping samples are requested at Day 1 (pre-dose), 24 hours / Day 2 (±1 hours) and 48 hours / Day 3 (±2 hours) after start of infusion in Cycles 1 and 2. Furthermore, immune phenotyping samples will be taken pre-dose in Cycles 1 and 2 at Day 8 and Day 15 and pre-dose for every second cycle starting from Cycle 3 (e.g., Cycle 3, 5, 7, etc.) including time of disease progression or treatment discontinuation. Samples can also be taken at an unscheduled visit.
- 5 T-cell receptor (TCR) profiling (blood) samples are requested at Cycle 1 Day 1 (pre-dose), and at Cycle 3 Day 1 (pre-dose) and at time of disease progression or treatment discontinuation. Samples can also be taken at an unscheduled visit.
- 6 After C3D1, PBMCs (for immune phenotyping and TCR profiling) will no longer be collected. Collection of PMBCs at treatment discontinuation and/or unscheduled visits is only required if the patient discontinues trial treatment prior to C3D1.

Table 1-8:	Biomarker table – in Part 1B

Treatment Cycle	Screening		Cycle 1-2				Cycle 3-N	Treatment discontinuation	Unscheduled
Day/Week	≤21 days prior to Visit C1 (D1)	D1	D2	D3	D8	D15	D16	-	-
Visit window		-		1h	±D1	±D1	±D3	-	-
Tissue compartment									
Tumor FFPE sample	$X^1$								
Tumor biopsy	$X^2$						$X^2$	$X^2$	$X^2$
Blood compartment									
Cytokines					$X^3$			$X^3$	$X^3$
Immune Phenotyping		$X^4$		X 	X 	X 	$X^4$	$X^4$	X 
TCR profiling		X 					X 	X 	X 

- 1 A formalin-fixed paraffin-embedded (FFPE) tumor tissue sample (for e.g., immunohistochemistry, tumor mutational burden) must be obtained from each patient from the latest available archival tumor tissue. If such tissue cannot be provided, the sponsor approval of enrollment is needed. Details regarding the preparation of slides and number of slides to be prepared will be described in the lab manual.
- 2 An optional fresh tumor biopsy (aspirates are not acceptable), which is collected before Cycle 1 Day 1, preferably derived from advanced stage disease. This biopsy needs to contain tumor tissue and is taken after failure/stop of last prior treatment at screening or before first administration of BNT411. Additionally, biopsies should be collected at Week 6 ([+7 days], i.e., after 2 cycles of BNT411) and at disease progression or treatment discontinuation if it is considered feasible without a risk of complications for the patient. If deemed necessary by the investigator, the patient may be called in for an unscheduled visit, optional additional tumor biopsies may be collected if patients have unscheduled biopsies or tumor tissue resection during the course of the trial. Details to the preparation of fresh tumor biopsies will be described in the lab manual.
- 3 Cytokine samples will be taken at the same time points given for PK sampling with the exception of "end of infusion"—please refer to Table 1-4. Furthermore, cytokine samples will be taken at disease progression or treatment discontinuation. If an adverse event (AE) of cytokine release syndrome (CRS) is suspected, cytokines should be obtained at an unscheduled visit to confirm diagnosis.
- 4 Immune phenotyping samples are requested at D1 (pre-dose) and at D3 i.e. 48 hours (±2 hours) after start of infusion of BNT411 in Cycles 1 and 2. Furthermore, immune phenotyping samples will be taken pre-dose in Cycles 1 and 2 at Day 8 and Day 15 and pre-dose (D1) for every second cycle starting from Cycle 3 (e.g. Cycle 3, 5, 7, etc.) including time of disease progression or treatment discontinuation. Samples can also be taken at an unscheduled visit.
- 5 T-cell receptor (TCR) profiling (blood) samples are requested at Cycle 1 Day 1 (pre-dose), and at Cycle 3 Day 1 (pre-dose) and at time of disease progression or treatment discontinuation. Samples can also be taken at an unscheduled visit.
- 6 After C3D1, PBMCs (for immune phenotyping and TCR profiling) will no longer be collected. Collection of PMBCs at treatment discontinuation and/or unscheduled visits is only required if the patient discontinues trial treatment prior to C3D1.

